## **Background and Rationale**

Two randomized trials published in 2002 found improved mortality and neurologic morbidity among out-of-hospital cardiac arrest (OHCA) victims with initial shockable rhythms (pulseless ventricular tachycardia and ventricular fibrillation) treated with therapeutic hypothermia targeting a temperature of 32°C-33°C as compared to placebo. A more recent, larger randomized trial comparing temperature controlled to 33°C vs 36°C did not demonstrate a significant difference in outcomes. In the earlier therapeutic hypothermia studies, neuromuscular blockade (NMB) was administered throughout the cooling period in the intervention group but not the control group. In contrast, paralytic use was minimized in both groups in the more recent study comparing 33°C to 36°C. Thus, the use of NMB is a potential unrecognized confounder from the earlier hypothermia studies.

Multicenter observational data has previously demonstrated that continuous NMB following cardiac arrest may be associated with improved lactate clearance and reduced mortality. NMB may improve post-cardiac arrest outcomes through a number of mechanisms including the reduction of global oxygen consumption, prevention of patient-ventilator dyssynchrony, reduction of metabolic demand, reduction of inflammation, or other unidentified pathways. The presently reported phase II trial, in addition to a similar phase II trial published by an affiliated cardiac arrest clinical trials group in South Korea, tested the hypothesis that early, continuous neuromuscular blockade following cardiac arrest will improve blood lactate levels and potentially clinical outcomes as compared to usual care.

# Study Overview

# Study Design and Setting

This was a phase II, multi-center, randomized trial of continuous neuromuscular blockade using rocuronium vs. usual care in patients who had sustained return of spontaneous circulation (ROSC) but remained unresponsive after cardiac arrest. Enrolling sites were five urban tertiary care centers in the United States. The trial coordinating center gathered and analyzed the data, and vouches for the accuracy and completeness of the data and for the fidelity of the trial to the protocol. Written informed consent was obtained from the legally authorized representatives of all patients.

# Trial Participants

Adult patients (aged ≥18 years) who experienced a cardiac arrest and subsequently had sustained ROSC (≥20 minutes) but remained comatose (i.e. not following commands) and were undergoing TTM targeting between 32°C and 36°C were enrolled in the study. An additional inclusion criterion of a minimum serum lactate level of ≥2mmol/L was added after the  $42^{nd}$  patient was enrolled. Patients were excluded if they had a traumatic etiology of cardiac arrest, were already receiving continuous neuromuscular blockade for clinical purposes, were not expected by the physician team to survive 24-hours, had been undergoing TTM for ≥6 hours, had a pre-arrest modified Rankin scale score of 4 or higher, or were members of a protected population (including prisoners, pregnant patients, and the developmentally disabled). Patients who had received a single-dose of a neuromuscular blocking agent, most commonly during

tracheal intubation, could be enrolled in the study so long as the drug had worn off and there were no immediate plans for additional neuromuscular blockade administration.

Patient flow through the trial will be displayed in a CONSORT diagram (see Appendix Figure 1 for shell figure).

## Randomization and Intervention

Patients were randomized to continuous NMB or usual care in blocks of four and in a 1:1 ratio. The randomization was stratified by study site and by the presence of shock, defined as the use of any vasopressor at the time of randomization. The random sequence was generated by an independent statistician who was not involved in the conduct of the study. The site-specific allocation sequences were maintained by the research pharmacies at each site for the duration of the study.

Patients in the continuous NMB arm received a rocuronium bolus of 1.0mg/kg followed by a continuous infusion of rocuronium for a total of 24-hours. The infusion of rocuronium was titrated to 1-2 out of 4 twitches on a train-of-four peripheral nerve stimulator. To minimize any difference in the time between randomization and receipt of the study drug between the two groups, patients in the usual care arm were administered a small volume of normal saline to mark the 0-hour time point. All patients undergoing TTM, including those who received continuous NMB, were deeply sedated per local site protocol. Use of the Columbia anti-shivering protocol was recommended to clinical teams, but adherence was not mandated.

## Study Registration and Monitoring

The trial was registered at clinicaltrials.gov (NCT02260258) and was approved by the institutional review boards of all enrolling institutions.

A Data Safety and Monitoring Board (DSMB) evaluated and monitored the trial for safety. There were no pre-specified stopping rules for futility or efficacy. No statistical interim analyses were performed.

# **Outcomes and Definitions**

## Primary Outcome and Sample Size Estimation

The primary outcome of the study is change in serum lactate level measured between 0-hours and 24-hours after the receipt of study drug. This outcome was chosen as lactate is a continuous variable which is highly correlated with hospital survival in cardiac arrest patients. The 24-hour time point was selected as it was drawn after completion of the rocuronium infusion but not so late that a significant proportion of patients may have already died. Based on conservative estimates drawn from observational data, a sample size of 80 patients was specified to detect a predicted mean difference in 24-hour lactate of 2.0mmol/L (±3.2mmol/L) with 80% power assuming a two-sided test and an alpha of 0.05.

# Secondary Outcomes

- Lactate change between 0- and 12-hours after administration of study drug
- Lactate change between 0- and 36-hours after administration of study drug
- Shock-free days
  - Shock-free days measured as days alive and free of shock (<6 hours receiving a vasopressor) over the first 7 days after enrollment.

- Ventilator-free days
  - Ventilator-free days measured as days alive and free of invasive mechanical ventilation (<6 hours with an endotracheal tube) over the first 7 days after enrollment.
  - Length of initial Intensive Care Unit (ICU) stay truncated at 28-days
  - Includes only the initial stay in the ICU and does not include ICU readmission Length of initial hospital stay truncated at 28-days
    - Includes only the initial hospital stay and does not include any readmissions
- Survival to hospital discharge
  - Neurologic outcome at hospital discharge
    - As defined using the Modified Rankin Scale
- Biomarker measures (available at 0-hours and 24-hours)
  - o Interleukin (IL)-1β, IL-6, IL-8, IL-10, and TNF-α
  - Neuron specific enolase [NSE]
  - S100 calcium-binding protein B (S100B)
- Muscle weakness assessed using a modified Medical Research Council scale

A table of outcomes by treatment group will be included (see Appendix Table 3).

#### Statistical Analysis

#### General Principles

All initial analyses will be performed in a modified intention-to-treat (modified ITT) population, defined as all randomly assigned subjects who received any study drug (rocuronium or the saline time marker). The primary analysis for the outcome of lactate at 24-hours will be repeated in the per-protocol population including only those patients who were alive at 24-hours and received either 24-hours of continuous rocuronium (if so assigned) compared to those who received usual care without any neuromuscular blockade medication after the time 0-hour point.

#### **Baseline Characteristics**

A description of the baseline characteristics will be presented by treatment group (see Appendix Table 1). Categorical variables will be summarized by frequencies and percentages. Percentages will be calculated according to the number of patients for whom data are available. Continuous variables will be summarized using means (standard deviations, SD) or medians (interquartile range, IQR). Statistical tests will not be used to compare baseline characteristics between groups. A table describing sedative and off-protocol paralytic use in each arm will be included (Appendix Table 2)

#### Analysis of Primary Outcome

The primary outcome is lactate change between 0-hours and 24-hours after enrollment. The group difference in change from the time of study drug administration (0-hours) to 24-hours will be assessed using a linear mixed effects model. Lactate values will be log-transformed for this analysis if they are not approximately normally distributed. Fixed effects will include the allocated treatment, shock stratification, time point (0-hour, 12-hour, and 24-hour), and the interaction between treatment and time point. Study site will be included as a random intercept. The usual care group will be the reference variable for group, and baseline (0-hour) will be the

reference variable for time. Means and 95% confidence intervals of lactate over time will be presented, by treatment, using longitudinal plots (see appendix Figure 2)

## Analysis of Secondary Outcomes

The following outcomes will be summarized using mean  $\pm$  SD or median (IQR) and linear regression using the above described linear mixed model will be performed to assess the differences between treatment groups.

- ICU length of stay
- Hospital length of stay
- Time to shock reversal
- Time to liberation from mechanical ventilation
- Biomarker measures (regression controlled for baseline level of each biomarker)
- Muscle weakness score

The following outcomes will be summarized using frequencies and percentages and logistic regression will be performed to assess the differences between treatment groups.

- Neurologic outcome at hospital discharge
- Survival to hospital discharge

## Subgroup Analyses

The primary outcome analysis will be additionally performed in each of the below subgroups.

- Shock and non-shock stratification groups
- Shockable and non-shockable initial rhythms
- Cardiac arrest location

## Additional Planned Analyses

Additional planned analyses of total body oxygen consumption and cellular oxygen consumption for those patients in whom these variables are available will be performed.

## Statistical Software

Stata (version 14, StataCorp, College Station, Tx) will be used for all analyses.

## Appendix

Appendix Figure 1

Appendix Figure 2 - Change in Lactate over Time

Appendix Table 1 - Cohort Characteristics

Variable	NMB	Usual Care
Demographics		
Age (Median, IQR)		
Sex (%Female)		
Race (%White)		

Past Medical History	
Congestive heart failure	
Atrial fibrillation	
Coronary artery disease	
Prior cardiac arrest	
Chronic pulmonary disease	
Kidney disease	
Active malignancy	
Arrest Characteristics	
Location (%OHCA)	
Initial Rhythm (% Non- shockable)	
Estimated no-flow time (median, IQR)	
Estimated low-flow time (median, IQR)	
Arrest duration (minutes, median, IQR)	
Witnessed (%yes)	
Bystander CPR provided (%yes)	
Arrest etiology (%cardiac)	
Characteristics at Enrollment	
pH (median, IQR)	
pCO2 (median, IQR)	
pO2 (median, IQR)	
Shock stratification (% shock)	
STEMI present (%yes)	
Target temperature (median, IQR)	

Received any paralytic prior to enrollment (%yes)	

# Appendix Table 2 - Sedatives and Off-Protocol Paralytics

Variable	NMB				Usual	Care		
Sedation and Analgesia (% receiving)	0hr	12hr	24hr	36hr	0hr	12hr	24hr	36hr
Propofol								
Midazolam								
Lorazepam								
Dexmedetomidine								
Fentanyl								
Paralytic (% receiving)								
Bolus Rocuronium								
Continuous Rocuronium								
Bolus Cisatracurium								
Continuous Cisatracurium								

# Appendix Table 3 – Outcomes

Variable	NMB	Usual Care	Effect estimate (95% confidence interval)
Lactate Level (mmol/L, median, IQR)			
0-hour			
12-hour			
24-hour			
36-hour			
Clinical Outcomes			
ICU LOS (days, median, IQR)			

Hospital LOS (days, median, IQR)		
Discharge CPC ≤2 (%)		
Muscle Weakness Score (median, IQR)		
Hospital Survival (% survived)		

## Background and Rationale

Two randomized trials published in 2002 found improved mortality and neurologic morbidity among out-of-hospital cardiac arrest (OHCA) victims with initial shockable rhythms (pulseless ventricular tachycardia and ventricular fibrillation) treated with therapeutic hypothermia targeting a temperature of 32°C-33°C as compared to placebo. A more recent, larger randomized trial comparing temperature controlled to 33°C vs 36°C did not demonstrate a significant difference in outcomes. In the earlier therapeutic hypothermia studies, neuromuscular blockade (NMB) was administered throughout the cooling period in the intervention group but not the control group. In contrast, paralytic use was minimized in both groups in the more recent study comparing 33°C to 36°C. Thus, the use of NMB is a potential unrecognized confounder from the earlier hypothermia studies.

Multicenter observational data has previously demonstrated that continuous NMB following cardiac arrest may be associated with improved lactate clearance and reduced mortality. NMB may improve post-cardiac arrest outcomes through a number of mechanisms including the reduction of global oxygen consumption, prevention of patient-ventilator dyssynchrony, reduction of metabolic demand, reduction of inflammation, or other unidentified pathways. The presently reported phase II trial, in addition to a similar phase II trial published by an affiliated cardiac arrest clinical trials group in South Korea, tested the hypothesis that early, continuous neuromuscular blockade following cardiac arrest will improve blood lactate levels and potentially clinical outcomes as compared to usual care.

## Study Overview

### *Study Design and Setting*

This was a phase II, multi-center, randomized trial of continuous neuromuscular blockade using rocuronium vs. usual care in patients who had sustained return of spontaneous circulation (ROSC) but remained unresponsive after cardiac arrest. Enrolling sites were five urban tertiary care centers in the United States. The trial coordinating center gathered and analyzed the data, and vouches for the accuracy and completeness of the data and for the fidelity of the trial to the protocol. Written informed consent was obtained from the legally authorized representatives of all patients.

### *Trial Participants*

Adult patients (aged  $\geq 18$  years) who experienced a cardiac arrest and subsequently had sustained ROSC ( $\geq 20$  minutes) but remained comatose (i.e. not following commands) and were undergoing TTM targeting between 32°C and 36°C were enrolled in the study. An additional inclusion criterion of a minimum serum lactate level of  $\geq 2$ mmol/L was added after the 42nd patient was enrolled. Patients were excluded if they had a traumatic etiology of cardiac arrest, were already receiving continuous neuromuscular blockade for clinical purposes, were not expected by the physician team to survive 24-hours, had been undergoing TTM for  $\geq 6$  hours, had a pre-arrest modified Rankin scale score of 4 or higher, or were members of a protected population (including prisoners, pregnant patients, and the developmentally disabled). Patients who had received a single-dose of a neuromuscular blocking agent, most commonly during

tracheal intubation, could be enrolled in the study so long as the drug had worn off and there were no immediate plans for additional neuromuscular blockade administration.

Patient flow through the trial will be displayed in a CONSORT diagram (see Appendix Figure 1 for shell figure).

### *Randomization and Intervention*

Patients were randomized to continuous NMB or usual care in blocks of four and in a 1:1 ratio. The randomization was stratified by study site and by the presence of shock, defined as the use of any vasopressor at the time of randomization. The random sequence was generated by an independent statistician who was not involved in the conduct of the study. The site-specific allocation sequences were maintained by the research pharmacies at each site for the duration of the study.

Patients in the continuous NMB arm received a rocuronium bolus of 1.0mg/kg followed by a continuous infusion of rocuronium for a total of 24-hours. The infusion of rocuronium was titrated to 1-2 out of 4 twitches on a train-of-four peripheral nerve stimulator. To minimize any difference in the time between randomization and receipt of the study drug between the two groups, patients in the usual care arm were administered a small volume of normal saline to mark the 0-hour time point. All patients undergoing TTM, including those who received continuous NMB, were deeply sedated per local site protocol. Use of the Columbia anti-shivering protocol was recommended to clinical teams, but adherence was not mandated.

### *Study Registration and Monitoring*

The trial was registered at [clinicaltrials.gov](https://clinicaltrials.gov) (NCT02260258) and was approved by the institutional review boards of all enrolling institutions.

A Data Safety and Monitoring Board (DSMB) evaluated and monitored the trial for safety. There were no pre-specified stopping rules for futility or efficacy. No statistical interim analyses were performed.

## Outcomes and Definitions

### *Primary Outcome and Sample Size Estimation*

The primary outcome of the study is change in serum lactate level measured between 0-hours and 24-hours after the receipt of study drug. This outcome was chosen as lactate is a continuous variable which is highly correlated with hospital survival in cardiac arrest patients. The 24-hour time point was selected as it was drawn after completion of the rocuronium infusion but not so late that a significant proportion of patients may have already died. Based on conservative estimates drawn from observational data, a sample size of 80 patients was specified to detect a predicted mean difference in 24-hour lactate of 2.0mmol/L ( $\pm 3.2$ mmol/L) with 80% power assuming a two-sided test and an alpha of 0.05.

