### *Secondary Outcomes*

- Lactate change between 0- and 12-hours after administration of study drug
- Lactate change between 0- and 36-hours after administration of study drug
- Shock-free days
  - Shock-free days measured as days alive and free of shock (<6 hours receiving a vasopressor) over the first 7 days after enrollment.

- Ventilator-free days
  - Ventilator-free days measured as days alive and free of invasive mechanical ventilation (<6 hours with an endotracheal tube) over the first 7 days after enrollment.
- Length of initial Intensive Care Unit (ICU) stay truncated at 28-days
  - Includes only the initial stay in the ICU and does not include ICU readmission
- Length of initial hospital stay truncated at 28-days
  - Includes only the initial hospital stay and does not include any readmissions
- Survival to hospital discharge
- Neurologic outcome at hospital discharge
  - As defined using the Modified Rankin Scale
- Biomarker measures (available at 0-hours and 24-hours)
  - Interleukin (IL)-1 $\beta$ , IL-6, IL-8, IL-10, and TNF- $\alpha$
  - Neuron specific enolase [NSE]
  - S100 calcium-binding protein B (S100B)
- Muscle weakness assessed using a modified Medical Research Council scale

A table of outcomes by treatment group will be included (see Appendix Table 3).

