## Statistical Analysis

### *General Principles*

All initial analyses will be performed in a modified intention-to-treat (modified ITT) population, defined as all randomly assigned subjects who received any study drug (rocuronium or the saline time marker). The primary analysis for the outcome of lactate at 24-hours will be repeated in the per-protocol population including only those patients who were alive at 24-hours and received either 24-hours of continuous rocuronium (if so assigned) compared to those who received usual care without any neuromuscular blockade medication after the time 0-hour point.

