### *Analysis of Primary Outcome*

The primary outcome is lactate change between 0-hours and 24-hours after enrollment. The group difference in change from the time of study drug administration (0-hours) to 24-hours will be assessed using a linear mixed effects model. Lactate values will be log-transformed for this analysis if they are not approximately normally distributed. Fixed effects will include the allocated treatment, shock stratification, time point (0-hour, 12-hour, and 24-hour), and the interaction between treatment and time point. Study site will be included as a random intercept. The usual care group will be the reference variable for group, and baseline (0-hour) will be the

reference variable for time. Means and 95% confidence intervals of lactate over time will be presented, by treatment, using longitudinal plots (see appendix Figure 2)

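### The primary mixed model names only a site random intercept for lactates measured three times per patient, so as written its standard error for the 0–24 h treatment contrast is wrong; early deaths are a smaller, secondary gap.

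*SAP*

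**What the plan says.** The protocol and SAP carry the same text on this point.

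- **Outcome and time point** (SAP, Primary Outcome and Sample Size Estimation). The outcome is change in lactate from 0 to 24 hours. The 24-hour draw was preferred partly because it is "not so late that a significant proportion of patients may have already died". The sample size is 80, for a 2.0 mmol/L difference in 24-hour lactate (±3.2), 80% power, two-sided alpha 0.05.
- **Model** (SAP, Analysis of Primary Outcome). Fixed effects are treatment, shock stratum, "time point (0-hour, 12-hour, and 24-hour), and the interaction between treatment and time point". The 0-hour lactate is therefore an outcome row, not a covariate. The random part is one sentence: "Study site will be included as a random intercept". No patient effect, residual covariance structure or clustered standard error is mentioned.
- **Analysis set** (SAP, General Principles). The modified ITT set is everyone randomised who received any study drug, with no survival condition. Early death enters an analysis rule for this outcome only in the per-protocol repeat, "including only those patients who were alive at 24-hours".
- **Death elsewhere.** Patients who "were not expected by the physician team to survive 24-hours" are excluded (Trial Participants). Death is built into the shock-free outcome, "days alive and free of shock", and likewise into ventilator-free days (Secondary Outcomes).

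**The concern.** Each patient supplies both ends of the primary contrast. A model whose only random term is site treats those values, within a site, as if they came from different people. With complete data the point estimate is unaffected, because the treatment-by-24-hour term is still a difference of differences of cell means. The standard error, confidence interval and p-value are not. At stake is the one primary comparison in a trial of about 80 patients.

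The second issue is smaller. A patient who dies before 24 hours stays in the modified ITT set with a 0-hour and perhaps a 12-hour value. Without a patient-level term, those values say almost nothing about the missing 24-hour value, so survivors at 24 hours are set against everyone at baseline. The SAP gives reasons to think the loss may be informative: "lactate is a continuous variable which is highly correlated with hospital survival", and neuromuscular blockade (NMB) "may be associated with improved lactate clearance and reduced mortality".

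**Working it through.** **Inputs.** From the documents: 80 patients at 1:1 (40 per arm), difference 2.0, ±3.2 read as an SD, two-sided alpha 0.05. Assumed, because the documents give neither: the SDs at 0 and 12 hours, the within-patient correlations, and the early death rates.

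**1. The plan's own figure.** n per arm = 2(1.960 + 0.842)² × (3.2/2.0)² = 40.2, rounded up to 41 (82 in total). Power with 40 per arm is 79.8% (normal) or 78.8% (t test). So 80 matches a two-sample comparison of one value per patient with no loss.

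**2. Model as written, equal SDs.** The contrast is a difference of differences of four cell means.

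- Site-only SE = 3.2 × √(4/40) = 1.012, whatever the correlation ρ.
- True SE = 3.2 × √(4(1 − ρ)/40).
- Site-only power ≈ Φ[(2.0 − 1.96 × 1.012)/true SE]. Type I error = 2Φ[−1.96 × 1.012/true SE].

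| ρ | Reported SE | True SE | Type I error | Power as written | Power with correct SE |
|---|---|---|---|---|---|
| 0.3 | 1.012 | 0.847 | 1.9% | 51% | 66% |
| 0.5 | 1.012 | 0.716 | 0.6% | 51% | 80% |
| 0.7 | 1.012 | 0.554 | 0.03% | 51% | 95% |

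Fitted mixed models agree. At ρ = 0.5 (243 usable simulated trials per setting), the site-only model reported an SE of about 1.00 against an empirical 0.72–0.74. It rejected in 0.4% of trials with no effect and 56% at 2.0 mmol/L.

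**3. If ±3.2 is instead the SD of change.** The true SE is 3.2 × √(2/40) = 0.716, and the site-only SE is 0.716/√(1 − ρ) = 0.855, 1.012 or 1.306. Type I error is as in the table. Power as written is 67%, 51% or 22%, against 80% with the correct SE.

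**4. Unequal SDs.** The site-only model pools variance over the three times. Take SDs 5/2.5/2.5 and correlations 0.2 (0–12 h), 0.2 (12–24 h), 0.1 (0–24 h).

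- Pooled variance = (25 + 6.25 + 6.25)/3 = 12.5, so reported SE = √(12.5 × 4/40) = 1.118.
- True SE = √[(25 + 6.25 − 2 × 0.1 × 5 × 2.5) × 2/40] = 1.199.
- Type I error = 2Φ(−1.96 × 1.118/1.199) = 6.8%.

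Here the test is mildly anti-conservative. With correlations 0.4/0.5/0.3 and the same SDs the two nearly agree (1.12 against 1.09).

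**5. Would a patient random intercept do?** It assumes one common correlation and one variance.

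| SDs at 0/12/24 h | Correlations 0–12/12–24/0–24 h | Random-intercept SE | True SE | Type I error |
|---|---|---|---|---|
| 3.2/3.2/3.2 | 0.6/0.6/0.5 | 0.666 | 0.716 | 6.8% |
| 3.2/3.2/3.2 | 0.6/0.6/0.36 | 0.701 | 0.810 | 9.0% |
| 5/2.5/2.5 | 0.6/0.6/0.5 | 0.816 | 0.968 | 9.8% |

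The SE is √[(mean variance − mean covariance) × 4/40]. In the first row that is √[10.24 × (1 − 0.567) × 0.1] = 0.666.

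**6. Early deaths.** Assume 24-hour means of 5 (usual care) and 3 (NMB), SD 3.2, a true effect of −2.0, and logit(death) = −3.0 + b(24-hour lactate − 5) with b = 0.2, 0.3, 0.4. Deaths are 5.6%, 6.8%, 8.4% in usual care and 3.9%, 3.9%, 4.3% on NMB. The site-only contrast becomes −1.97, −1.92, −1.86, a bias of 0.03 to 0.14 mmol/L. When death depends on 12-hour lactate instead, a model using each patient's earlier values gives about −2.00. With no effect on either lactate or death, the bias is zero.

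**The case against.** **The text does not say site is the only random effect.** True. It names no other, and an analyst might add a patient term unprompted. The supportable statement is that the within-patient covariance is unspecified and that the model fitted literally is wrong. An analysis plan should not leave this to be guessed.

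**A reader might infer that the test is always conservative, or that it yields false positives.** Neither follows from the documents. The direction depends on variances and correlations that they do not give. Roughly equal variances with positive correlation make the test conservative. A much larger 0-hour variance with weak correlation can make it mildly liberal.

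**A reader might infer that early deaths seriously distort the primary result.** The documents do not support that. They give no early death rate, the eligibility rule and the choice of time point both work to keep such deaths few, and bias in the arm difference requires deaths that differ by arm in number or type. What stands is that neither safeguard says how a death is analysed.

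**Log transformation might rescue the model.** It may bring the variances closer together, but it does not make one patient's values independent.

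**Conclusion.** The concern holds, led by the covariance. As written, the primary model gives a wrong standard error for the 0–24 hour contrast. Under equal SDs of 3.2 and correlation 0.3 to 0.7, that standard error is 1.20 to 1.83 times too large and power is about 51% rather than 66% to 95%. These figures illustrate the size; they are not an estimate of the trial's actual power. The reversed case in step 4 is also possible.

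The missing rule for deaths before 24 hours is a real but secondary gap, worth about 0.03 to 0.14 mmol/L on a true −2.0 under the assumed 6–8% usual-care deaths. The point deserves correction because the analysis is the primary one and the remedy is cheap.

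**What to change.** In Analysis of Primary Outcome, in both documents:

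1. Keep the site random intercept and add an unstructured within-patient residual covariance over 0, 12 and 24 hours, with a separate variance at each time. Do not offer a patient random intercept alone as equivalent. Its type I error is about 7–10% when correlations decay or variances differ over time.
2. State that 24-hour values are assumed missing at random given the observed lactates, arm and shock stratum.
3. Add one modified ITT sensitivity analysis for deaths before 24 hours. One option ranks patients on 0–24 hour change with early death as the worst rank, labelled as a death-plus-lactate composite and kept secondary.
4. Optionally, restate the planned two-sample power as about 79% with 80 evaluable patients.

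The cost is SAP wording, a covariance specification and one extra analysis. The downsides are a few more covariance parameters with about 80 patients and a missing-at-random assumption that cannot be tested. It does not cover death that depends on the unmeasured 24-hour lactate, which is why step 3 is needed. Worst-rank scoring also loses power when deaths are unrelated to treatment. In simulation (correlation 0.5, true −2.0), it had 62% power against 76% for survivors' change with 8% random deaths per arm, and 40% against 70% with 20%. It should not replace the primary model.
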